1. PERIOD ALLOCATION OF ADVERSE EVENTS

Solicited events will always be allocated to the Post-dose 1 or Post-dose 2 period, as appropriate.

Unsolicited AEs will be allocated to the different periods per the following rules:

Step 1: Allocation of unsolicited events to the periods/phases:

The AEs present in the database are allocated to periods/phases based on their start date/time. If the start date/time of an event falls between (or on) the start and stop date/time of a period/phase, the AE is attributed to that period/phase (ie, AEs following vaccination).

Incomplete dates (ie, time and/or day and/or month and/or year missing):

- 1) In case of partial start or stop dates, the events are allocated to the periods/phases using the available partial information on start and end date; no imputation will be done. If, for instance, for the AE start date only month and year are available, these data are compared to the month and year information of the periods/phases. This rule may lead to multiplication of the event because of its assignment to multiple periods/phases (see below example).
- 2) In case of a completely missing start date, the event will be allocated to the appropriate period/phase (eg, Post-dose 1 or Post-dose 2) and consequently the Regimen period; except if the end date of the AE falls before the start of the Post-dose 1 or Post-dose 2 period.
- 3) In case of a completely missing end date (ie, only for the calculation of duration):
 - In case the AE is flagged as ongoing the date is imputed by the cut-off date of the analysis for subjects still ongoing in the study, and by the end date of the last period/phase for subjects who discontinued or completed the trial.
 - In case the AE is not flagged as ongoing, the end date is considered as unknown, and the date will remain missing.

Examples:

Screening Phase: start date: 14JUN2016 - stop date: 28JUN2016

Post-dose 1 period: start date: 28JUN2016 - stop date: 19JUL2016

1) Adverse event: start date: JUN2016- stop date: 15JUL2016

As the start date only has information about month and year, only this information will be used from the periods/phases (ie, assuming any day of Jun is possible) and therefore the AE will be assigned to the Screening Phase as well as to the Post-dose 1 period.

2) Adverse event: start date: JUL2016- stop date 14JUL2016

As the AE starts after the Screening Phase and after the start of the Post-dose 1 period, it is only assigned to the Post-dose 1 period.

Remarks:

- In addition to the date information, time information is considered to allocate AEs to periods, if available.

- The imputation of missing end dates of ongoing AEs will only be used to derive the duration of the event (ie, to give an indication of the minimum duration). The imputed end dates will not be shown in the data listings.

Step 2: Combination of events:

Overlapping/consecutive events are defined as events of the same subject with the same preferred term which have at least 1 day overlap or for which the start date of an event is 1 day after the end date of the preceding event. Overlapping/consecutive events may be combined into one AE or not, according to the following rules:

- 1) If overlapping/consecutive events start in a non-active phase (Screening or any of Post-dose FU phases) followed by an AE in an active (Post-dose 1 or Post-dose 2) period, they are allocated to their respective periods/phases and are considered as separate events.
- 2) In case overlapping/consecutive events start within a single period/phase, they are considered as one and the same AE. The individual events which contribute to this AE are retained as individual records in the Analysis Data Model (ADaM) database but are assigned the same onset, period/phase, and total duration.
- 3) In case overlapping/consecutive events start in an active period followed by a non-active phase, they are allocated only to the active period and are considered as one and the same AE. The individual events which contribute to this AE are retained as individual records in the ADaM database but are assigned the same onset, period, and total duration.
- 4) In case an active period is followed by another active period, and the overlapping/consecutive events start in both periods, they are allocated to their respective period and are considered as separate AEs. The same rule applies for 2 non-active phases.

- Remarks:
 1. Time is not considered when determining overlap of events.
 2. Events can only be combined into one and the same AE if their start and stop dates are known.
 3. In case the completely missing end date is imputed (for calculation of duration), this date is also considered as a complete date.

Examples:

Screening phase: start date: 14JUN2016 - stop date: 28JUN2016

Post-dose 1 period: start date: 28JUN2016 - stop date: 26JUL2016

Post-dose 1 FU phase: start date: 27JUL2016 - stop date: 15AUG2016

Example for the above Scenario 1

AE1: start date: 20JUN2016- stop date: 10JUL2016

AE2: start date: 08JUL2016- stop date: 18JUL2016

AE1 will be attributed to the Screening Phase and AE2 to the Post-dose 1 period.

Example for the above Scenario 3

AE1: start date: 18JUL2016- stop date: 28JUL2016

AE2: start date: 28JUL2016- stop date: 08AUG2016

As AE1 starts in the active period (Post-dose 1) and overlaps with AE2 which starts in a non-active phase (Post-dose 1 FU), this AE is considered as a single AE in the AE analysis starting on 18JUL2016 and ending on 08AUG2016 and is attributed to the Post-dose 1 period.

2. TRANSFORMING ON-SITE ASSESSMENTS AND DIARIES OF SOLICITED ADVERSE EVENTS INTO AN ANALYSIS FORMAT

When creating the analysis dataset for solicited AEs, solicited AEs (recorded by day) need to be converted into the format of unsolicited AEs (recorded by event). All diary data will be considered, as well as any post-dose on-site assessment (scheduled as well as unscheduled) within (including the day of vaccination) 8 days after vaccination. For solicited local AEs for which a diameter is measured, the maximum of diameter derived grade and investigator severity (if available) will be used. The start date of the AE will be considered as the date of first occurrence of the solicited AE (both local and systemic). If on subsequent day(s), the same grade is reported, the last reported date is used as the end date of the AE. A new record is created in case the grade of the event changes. If there is a time gap of at least one day between two (or more) occurrences of the same type of the solicited AE, then the second (and/or next) occurrence will be considered as a new AE. In case no data is reported for a day, this is analyzed as no event reported. If the on-site assessment differs in grade or relatedness (if collected) with the corresponding diary data, only the highest grade and relatedness assessment indicating the highest relatedness to study vaccination per AE will be kept in the analysis database and used in the tables and listings. The following example shows how the solicited AE should be converted into a format of unsolicited AEs:

Data from the Subject Diary

Subject: 0001

Solicited systemic AE: Headache

	On-site Assessment	Diary Data							
		Day 1 01Jan16	Day 1 01Jan16	Day 2 02Jan16	Day 3 03Jan16	Day 4 04Jan16	Day 5 05Jan16	Day 6 06Jan16	Day 7 07Jan16
Solicited AE									
Grade	2	1	1	0	3	3	1	0	0
Relatedness	Doubtful	Probable							

The data should be converted and stored in the AE dataset as follows:

Subject No.	AE	Start Date (Char)	Stop Date (Char)	Severity	Relatedness	AEID
0001	Headache	01Jan16	02Jan16	2	Probable	1
0001	Headache	04Jan16	05Jan16	3	Probable	1
0001	Headache	06Jan16	06Jan16	1	Probable	1

If a solicited AE ends after Day 8:

The stop date of the event is the “Date of last day of symptom” as recorded in the eCRF and the “maximum severity” after Day 8 as recorded in the CRF. A separate record is created for this, in case this severity deviates from the previous record.

Note: To complete the start and end-date based on diary data, the date will be calculated based on the day the AE is reported relative to vaccination and not on the reported date. For example, if the vaccination is on 01-JAN-2016, and the AE starts on Day 3, the start date will be set to the 03-JAN-2016, independent of the reported actual date.

For the calculation of duration, the first and last day is used, irrespective of whether interruptions occurred in between by missing reporting days or Grade 0 events. In the above example, the 4 records contribute to the same AE, therefore AEID is set to the same value and the duration of the AE is set to 6 for all records.

It is important to note that the occurrence of solicited injection site reaction and/or solicited systemic adverse events considered to be related to the study vaccine and persisting for at least 3 days will result in a study pause. However, the above rule for calculating duration of AEs may incorrectly indicate that the pausing rule is met. Therefore, a listing of subjects with Grade 3 (severe) AEs will be generated with an indication that interruption between AE start and AE end are not considered in the calculation of the duration of the AEs.

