Regimen*	Post-dose 1	Date and time of Dose 1 administration	Minimum of: a) 23:59 on the date of last contact (for early study discontinuations) b) 23:59 on the date of relative Day 29 Post-dose 1 c) one minute prior to Dose 2 administration d) 23:59 on the date of database cut-off (in case of interim analysis)
Post-dose 1 FU		One minute after the end of the Post-dose 1 period	Minimum of: a) 23:59 on the date of last contact (for early study discontinuation or completion) b) one minute prior to Dose 2 administration c) 23:59 on the date of database cut-off (in case of interim analysis)
Regimen*	Post-dose 2	Date and time of Dose 2 administration	Minimum of: a) 23:59 on the date of last contact (for early study discontinuation or completion) b) 23:59 on the date of relative Day 29 Post-dose 2 c) 23:59 on the date of database cut-off (in case of interim analysis) Note: subjects who do not receive Dose 2 will not have a Post-dose 2 period.
Post-dose 2 FU		One minute after the end of the Post-dose 2 period	Minimum of: a) 23:59 on the date of database cut-off (in case of interim analysis) b) 23:59 on the date of last contact (for early study discontinuation or completion)
Regimen*	Post-dose 3	Date and time of Dose 3 administration	Minimum of: a) 23:59 on the date of last contact (for early study discontinuation or completion) b) 23:59 on the date of relative Day 29 Post-dose 3 c) 23:59 on the date of database cut-off (in case of interim analysis) Note: subjects who do not receive Dose 3 will not have a Post-dose 3 period.

Post-dose 3 FU		One minute after the end of the Post-dose 3 period	Minimum of: a) 23:59 on the date of database cut-off (in case of interim analysis) b) 23:59 on the date of last contact (for early study discontinuation or completion)
-------------------	--	--	---

Note 1: * Regimen period includes both the Post-dose 1, Post-dose 2 and Post-dose 3 periods.

Note 2: FU = follow-up.

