7.1.3. Analysis Methods

In general, the AEs following vaccination will be summarized (ie, tables of descriptive statistics) by vaccination schedule and presented per period/phase. Similar summary tables will also be provided pooled by vaccine (dose).

Furthermore, unsolicited AEs will be summarized (showing number and percentage) by System Organ Class (SOC) and Preferred Term (PT). Solicited AEs (recorded by day) will be converted into the analysis format of unsolicited AEs (recorded by event) as detailed in Attachment 2. These solicited AEs will be summarized by class (local, systemic) and Preferred Term. For solicited as well as unsolicited AEs, tables focusing on severity will be created. Focus will also be on the relationship (to the study vaccine) of the solicited systemic and unsolicited AEs.

The SAEs, AEs with fatal outcome, AEs leading to permanent discontinuation from study vaccination, Grade 3 AEs and IREs will also be listed. A table summarizing all those parameters will further be created and presented per analysis period and vaccination schedule. Summary tabulations by SOC and PT for each of the category of events (ie, SAEs, AEs with fatal outcome, AEs leading to permanent discontinuation from boost vaccination, Grade 3 AEs and immediate reportable events) will also be generated on the entire reporting period. Subject narratives will be generated for these events, except Grade 3 AEs. For Grade 3 AEs, the narratives will only be generated for those AEs that are considered related to study vaccination.

For the solicited local and systemic AEs, the duration and time to first onset of the events will also be summarized. If a subject experiences more than 1 occurrence of a solicited event, the maximum duration of the events will be used. The time to first onset is defined as:

$$[\text{date of first onset} - \text{reference date} + 1]$$

The reference date is the start date of each vaccination period (ie, Post-dose 1, Post-dose 2 or Post-dose 3). Duration and time to onset of AEs will be expressed in days.

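### SAP Attachment 2 defines a solicited-AE episode in two incompatible ways (its own example is 6 days and one AE, or 3 days and two AEs), and SAP Section 7 does not restate the protocol's solicited-AE denominator

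*SAP*

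**What the plan says.** Solicited local and systemic events are a primary endpoint (Protocol Section 11.1.1). SAP Section 7.1.3 plans a duration summary: "For the solicited local and systemic AEs, the duration and time to first onset of the events will also be summarized". It adds: "If a subject experiences more than 1 occurrence of a solicited event, the maximum duration of the events will be used".

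SAP Attachment 2 converts daily diary entries into events. Its rules are:

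- Change of grade: "A new record is created in case the grade of the event changes".
- Break of a day or more between occurrences of the same event type: "then the second (and/or next) occurrence will be considered as a new AE".
- Unreported day: "In case no data is reported for a day, this is analyzed as no event reported".
- On-site and diary data differ: "only the highest grade and relatedness assessment indicating the highest relatedness to study vaccination per AE will be kept in the analysis database".
- Duration, stated after the worked example: "the first and last day is used, irrespective of whether interruptions occurred in between by missing reporting days or Grade 0 events".

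The worked example has a Grade 0 entry on Day 3. All printed rows share event identifier 1, and the text assigns a duration of 6 to every record. The text refers to four records; the table shows three rows.

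On the denominator, Protocol Section 11.5 analyses solicited events only in Full Analysis set subjects who have reactogenicity assessments. SAP Section 7 names the full analysis set and leaves out only subjects who did not receive the dose in question. SAP Section 3, which lists departures from the protocol analysis, does not mention this.

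**The concern.** The break rule creates a new event after one symptom-free day. The duration rule and the identifier in the example treat what lies on both sides of that day as the same event. If the second reading governs, the maximum rule in Section 7.1.3 has nothing to choose from within a dose period. It can then act only between doses, in the combined period ("Regimen period includes both the Post-dose 1, Post-dose 2 and Post-dose 3 periods").

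Two programmers could therefore follow different sentences of the same SAP and report different durations from one diary. Under the first-to-last rule, a reaction that returns after a clear or unreported day is shown as one longer reaction, and a short Grade 3 run carries the duration of the whole span. The SAP concedes that its rule can wrongly suggest that the pausing criterion was met, and it adds an annotated Grade 3 listing. The duration summary itself carries no such label.

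The denominator gap matters because, on the full analysis set and with unreported days read as no event, a vaccinated subject without any diary would be counted as free of reactions.

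**Working it through.** **Inputs.** From the SAP Attachment 2 example: on-site grade 2 on Day 1; diary grades for Days 1 to 8 of 1, 1, 0, 3, 3, 1, 0, 0. Symptom days are 1, 2, 4, 5 and 6.

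**The plan's own figure.** Duration = last day − first day + 1 = 6 − 1 + 1 = 6, with one event. This reproduces the SAP.

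**Break rule plus Section 7.1.3.** Day 3 is Grade 0, so there are two occurrences: Days 1–2 (2 days) and Days 4–6 (3 days). The summary takes max(2, 3) = 3, with two events.

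| Quantity | First-to-last rule | Break rule + Section 7.1.3 |
|---|---|---|
| Events in the example | 1 | 2 |
| Duration summarised | 6 days | 3 days |
| Time to first onset | Day 1 | Day 1 |
| Worst grade | 3 | 3 |

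The Grade 3 run is Days 4–5, or 2 days, but its record carries duration 6.

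**Record count.** If the on-site grade replaces only the Day 1 diary grade, the runs are Day 1 (Grade 2), Day 2 (Grade 1), Days 4–5 (Grade 3) and Day 6 (Grade 1): four records. If it replaces the grade of the whole Day 1–2 record, the runs are Days 1–2 (Grade 2), Days 4–5 (Grade 3) and Day 6 (Grade 1): three records, as printed. Text and table therefore imply different override rules.

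**Size in general.** For two runs of a and b days separated by one day, the span is a + b + 1 and the longest run is max(a, b), so the excess is min(a, b) + 1. With a + b ≤ 7 in an 8-day diary, the excess is 2 to 4 days. For example, an event on Days 1 and 3 with Day 2 unreported lasts 1 day or 3 days (a = b = 1, excess 2). There are 255 non-empty 8-day patterns. Of these, 36 are uninterrupted, leaving 255 − 36 = 219 interrupted ones, with an excess from 2 days (36 patterns) to 7 days (8 patterns). These are counts of patterns, not probabilities.

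**Denominator.** Rate on the full analysis set = rate among assessed × (1 − share without data). The documents give no such share. Assuming 2%, 5% or 10%, a rate of 50% among assessed subjects becomes 49.0%, 47.5% or 45.0%.

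**The case against.** The best defence is that the first-to-last rule is explicit and specific. It is stated for duration, names both Grade 0 and missing days, and is worked through to 6. Attachment 2 also uses the term AE for a same-grade run, so a new AE after a break could mean only a new row. Read this way, the handling of unreported days is a general rule with a stated exception for duration. The maximum rule still works across doses. The rationale for the current SAP version says that tables count a solicited event once within an analysis period. The limitation is disclosed, and a long span is the cautious direction for safety.

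Much of this stands. A reader might infer that the longest uninterrupted occurrence is the correct duration and that the first-to-last rule is simply an error. The documents do not support that. The first-to-last rule is a deliberate choice, and after Day 8 only the last symptom date and the maximum severity are recorded, so a longest run cannot be seen for longer reactions. A reader might also infer that the stated four records is the mistake; the override sentence fits either count.

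The defence does not remove the conflict. The SAP nowhere says that one sentence overrides the other, and Section 7.1.3 does not confine its maximum to comparisons across doses. Once-per-period counting concerns grade and relatedness in the tables, not duration. Attachment 1, written for unsolicited events, joins only events that overlap or follow on the next day; an event starting on 4 January would not join one that ended on 2 January.

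On the denominator, the SAP's silence does not revoke the protocol rule. A reader might infer a deliberate change, but the text shows only an omission.

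**Conclusion.** The inconsistency is real and visible in the SAP's own example: 6 days and one event, or 3 days and two events, with four records stated and three printed. It should be corrected, but its reach is narrow. It changes the descriptive duration summary and any count of events rather than subjects. It leaves unchanged the number of subjects with a solicited event, worst grade and time to first onset. Real-time pausing under Protocol Section 9.3.2 rests on ongoing review by the investigators and the medical monitor, not on this dataset. No hypothesis is tested, and the same rule applies in every arm.

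The size in the trial depends on how often reactions are interrupted, which the documents do not give. The documents also do not settle which of the two definitions should prevail. The denominator omission is a separate, lesser matter. Its effect is probably small, because Protocol Section 9.3.1 has the diary completed on site at the 7-day visit, and it cannot be computed; the percentages above rest on assumed shares.

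**What to change.** Adopt one episode definition for both the event identifier and the duration summary, and align Section 7.1.3, the Attachment 2 rules and the example with it. Either of these would do:

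1. **Split at breaks.** Each occurrence gets its own identifier and the longest is summarised per dose period. State how events that continue past Day 8 are handled, since interruptions are not recorded there. The example then reads two identifiers and 3 days.
2. **Keep first-to-last.** Label the summary as a span that includes symptom-free and unreported days, delete or reword the new-AE sentence, and state that the maximum in Section 7.1.3 applies only across doses. The example keeps one identifier and 6 days.

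Under either option, state whether the Day 1 on-site grade replaces Day 1 only (four records) or the whole Day 1–2 record (three records), and make text and table agree. Reporting days at Grade 3 separately (2 in the example) is optional.

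In SAP Section 7, restate the Protocol Section 11.5 denominator for solicited events, per dose, and show that n. If a change is intended, list it in Section 3.

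The cost is SAP wording and minor reprogramming, with no new data. Under option 1 durations will read shorter, and an unreported day can split a reaction that was in fact continuous; the span can be kept as a labelled supplement to show this.

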3. TOXICITY TABLES FOR USE IN TRIALS ENROLLING HEALTHY ADULTS

The abbreviations used in the following tables are:

ALT: alanine aminotransferase; aPTT: activated partial thromboplastin time; AST: aspartate aminotransferase; AV block: atrioventricular block; bpm: beats per minute; CK: creatine kinase; FEV₁: forced expiratory volume in 1 second; g: gram; HI: high; HPF: high power field; INR: international normalized ratio; IV: intravenous; LO: low; mEq: milliequivalent; mm Hg: millimeter of mercury; N: not graded; PT: prothrombin time; PTT: partial thromboplastin time; QTc: QT-interval corrected for heart rate; QTcB: Bazett's corrected QT interval; QTcF: Fridericia's corrected QT interval; RBC: red blood cell; Rx: therapy; ULN: upper limit of normal

CLINICAL ADVERSE EVENTS

Grading scale used for clinical adverse events is adapted from the Division of Microbiology and Infectious Diseases (DMID) Toxicity Tables (2014). For adverse events not included in the tables below, refer to the severity criteria guidelines in Section 12.1.3 of the CTP¹.

Cardiovascular	Grade 1	Grade 2	Grade 3
Arrhythmia		Asymptomatic, transient signs, no Rx required	Recurrent/persistent; symptomatic Rx required
Hemorrhage, blood loss	Estimated blood loss ≤ 100 mL	Estimated blood loss > 100 mL, no transfusion required	Transfusion required

QTcF (Fridericia's correction) ^a or QTcB (Bazett's correction)	Asymptomatic, QTc interval 450-479 ms, OR Increase in interval <30 ms above baseline	Asymptomatic, QTc interval 480-499 ms, OR Increase in interval 30-60 ms above baseline ^b	Asymptomatic, QTc interval ≥500 ms, OR Increase in interval ≥60 ms above baseline
PR interval (prolonged)	PR interval 0.21-0.25 s	PR interval >0.25 s	Type II 2nd degree AV block OR Ventricular pause >3.0 s
Respiratory	Grade 1	Grade 2	Grade 3
Cough	Transient; no treatment	Persistent cough	Interferes with daily activities
Bronchospasm, acute	Transient; no treatment; FEV ₁ 71%-80% of peak flow	Requires treatment; normalizes with bronchodilator; FEV ₁ 60%-70% (of peak flow)	No normalization with bronchodilator; FEV ₁ <60% of peak flow
Dyspnea	Does not interfere with usual and social activities	Interferes with usual and social activities, no treatment	Prevents daily and usual social activity or requires treatment
Gastrointestinal	Grade 1	Grade 2	Grade 3
Nausea/vomiting	Minimal symptoms; caused minimal or no interference with work, school or self-care activities	Notable symptoms; required modification in activity or use of medications; did not result in loss of work or cancellation of social activities	Incapacitating symptoms; required bed rest and/or resulted in loss of work or cancellation of social activities
Diarrhea	2-3 loose or watery stools or <400 g/24 hours	4-5 loose or watery stools or 400-800 g/24 hours	6 or more loose or watery stools or >800 g/24 hours or requires IV hydration
Reactogenicity	Grade 1	Grade 2	Grade 3
Local reactions			
Pain/tenderness at injection site	Aware of symptoms but easily tolerated; does not interfere with activity; discomfort only to touch	Notable symptoms; required modification in activity or use of medications; discomfort with movement	Incapacitating symptoms; inability to do work or usual activities; significant discomfort at rest
Erythema/redness ^c	2.5-5 cm	5.1-10 cm	>10 cm
Induration/swelling ^d	2.5-5 cm and does not interfere with activity	5.1-10 cm or interferes with activity	>10 cm or prevents daily activity
Itching at the injection site	Minimal symptoms; caused minimal or no interference with work, school or self-care activities	Notable symptoms; required modification in activity or use of medications; did not result in loss of work or cancellation of social activities	Incapacitating symptoms; required bed rest and/or resulted in loss of work or cancellation of social activities

^a Inclusion dependent upon protocol requirements.

^b The Grade 2 increase in interval is changed from 30-50 ms to 30-60 ms since the original DMID Toxicity Tables (2014) did not cover the increase in interval between 50 and 60 ms.

^c In addition to grading the measured local reaction at the greatest single diameter, the measurement should be recorded as a continuous variable.

^d Induration/swelling should be evaluated and graded using the functional scale as well as the actual measurement.

Systemic reactions				
Allergic reaction	Pruritus without rash	Localized urticaria	Generalized urticaria; angioedema or anaphylaxis	
Headache	Minimal symptoms; caused minimal or no interference with work, school or self-care activities	Notable symptoms; required modification in activity or use of medications; did not result in loss of work or cancellation of social activities	Incapacitating symptoms; required bed rest and/or resulted in loss of work or cancellation of social activities	
Fatigue/malaise	Minimal symptoms; caused minimal or no interference with work, school or self-care activities	Notable symptoms; required modification in activity or use of medications; did not result in loss of work or cancellation of social activities	Incapacitating symptoms; required bed rest and/or resulted in loss of work or cancellation of social activities	
Myalgia	Minimal symptoms; caused minimal or no interference with work, school or self-care activities	Notable symptoms; required modification in activity or use of medications; did not result in loss of work or cancellation of social activities	Incapacitating symptoms; required bed rest and/or resulted in loss of work or cancellation of social activities	
Arthralgia	Minimal symptoms; caused minimal or no interference with work, school or self-care activities	Notable symptoms; required modification in activity or use of medications; did not result in loss of work or cancellation of social activities	Incapacitating symptoms; required bed rest and/or resulted in loss of work or cancellation of social activities	
Chills	Minimal symptoms; caused minimal or no interference with work, school or self-care activities	Notable symptoms; required modification in activity or use of medications; did not result in loss of work or cancellation of social activities	Incapacitating symptoms; required bed rest and/or resulted in loss of work or cancellation of social activities	

LABORATORY TOXICITY GRADING

Grading scale used for lab assessments is based on 'FDA's Toxicity Grading Scale for Healthy Adult and Adolescent Volunteers Enrolled in Preventive Vaccine Clinical Trials', but grade 3 and 4 are pooled below, consistent with the 3 scale toxicity grading used throughout the protocol. If a laboratory value falls within the grading as specified below but also within the local laboratory normal limits, the value is considered as normal. For hemoglobin only the change from reference is used for the grading. The FDA table does not include toxicity grading for hematocrit, RBC counts or INR.

Blood, Serum, or Plasma Chemistries ^a	LO/HI/N ^b	Mild (Grade 1)	Moderate (Grade 2)	Severe (Grade 3)
Sodium (mEq/L or mmol/L)	LO	132-134	130-131	≤129

^a Depending upon the laboratory used, reference ranges, eligibility ranges and grading may be split out by sex and/or age.

^b Low, High, Not Graded.

	HI	144-145	146-147	≥ 148
Potassium (mEq/L or mmol/L)	LO	3.5-3.6	3.3-3.4	≤ 3.2
	HI	5.1-5.2	5.3-5.4	≥ 5.5
Glucose (mg/dL)	LO	65-69	55-64	≤ 54
	HI ^a	100-110	111-125	>125
	HI ^b	110-125	126-200	>200
Blood urea nitrogen (mg/dL)	HI	23-26	27-31	>31
Creatinine (mg/dL)	HI	1.5-1.7	1.8-2.0	>2.0
Calcium (mg/dL)	LO	8.0-8.4	7.5-7.9	<7.5
	HI	10.5-11.0	11.1-11.5	>11.5
Magnesium (mg/dL)	LO	1.3-1.5	1.1-1.2	<1.1
Phosphorus (mg/dL)	LO	2.3-2.5	2.0-2.2	<2.0
CK (mg/dL)	N	1.25-1.5 x ULN	1.6-3.0 x ULN	$\geq 3.1 x$ ULN
Albumin (g/dL)	LO	2.8-3.1	2.5-2.7	<2.5
Total protein (g/dL)	LO	5.5-6.0	5.0-5.4	<5.0
Alkaline phosphatase (U/L)	N	1.1-2 x ULN	2.1-3 x ULN	$>3 x$ ULN
AST (U/L)	HI	1.1-2.5 x ULN	2.6-5 x ULN	$>5 x$ ULN
ALT (U/L)	HI	1.1-2.5 x ULN	2.6-5 x ULN	$>5 x$ ULN
Bilirubin, serum total (mg/dL) – when accompanied by any increase in Liver Function Test		1.1-1.25 x ULN	1.26-1.5 x ULN	$>1.5 x$ ULN
Bilirubin, serum total (mg/dL) – when Liver Function Test is normal		1.1-1.5 x ULN	1.6-2.0 x ULN	$>2.0 x$ ULN
Amylase (U/L)	N	1.1-1.5 x ULN	1.6-2.0 x ULN	$>2.0 x$ ULN
Lipase (U/L)	N	1.1-1.5 x ULN	1.6-2.0 x ULN	$>2.0 x$ ULN
Hematology				
	LO/HI/N ^c	Mild (Grade 1)	Moderate (Grade 2)	Severe (Grade 3)
Hemoglobin (women) change from baseline (g/dL)	LO	Any decrease- 1.5	1.6-2.0	>2.0
Hemoglobin (men) change from baseline (g/dL)	LO	Any decrease- 1.5	1.6-2.0	>2.0
White blood cell count (cell/mm ³)	HI	10,800-15,000	15,001-20,000	$>20,000$
	LO	2,500-3,500	1,500-2,499	$<1,500$
Lymphocytes (cell/mm ³)	LO	750-1,000	500-749	<500
Neutrophils (cell/mm ³)	LO	1,500-2,000	1,000-1,499	<1000
Eosinophils (cell/mm ³)	HI	650-1500	1501-5000	>5000
Platelets (cell/mm ³)	LO	125,000- 140,000	100,000- 124,999	$<100,000$
Coagulation				
PT (seconds)	HI	1.0-1.10 x ULN	1.11-1.20 x ULN	$>1.20 x$ ULN
International Normalized Ratio (INR) ^d	HI	1.1-1.5 x ULN	1.6-2.0 x ULN	$>2.0 x$ ULN
PTT or aPTT (seconds)	HI	1.0-1.2 x ULN	1.21-1.4 x	$>1.4 x$ ULN

^a Fasting.^b Non-fasting.^c Low, High, Not Graded.^d For INR, the values in the table are based on the Division of AIDS Table for Grading the Severity of Adult and Pediatric Adverse Events, 2009.

			ULN	
Fibrinogen (mg/dL)	HI	400-500	501-600	>600
	LO	150-200	125-149	<125
Urine				
Protein (dipstick)	HI	Trace	1+	2+
Glucose (dipstick)	HI	Trace	1+	2+
Blood (microscopic) - red blood cells per high power field (RBC/HPF)	HI	1-10	11-50	>50 and/or gross blood

RANGES TO CONVERT FDA SCALE (mg/dL) TO SI UNITS

Blood, Serum, or Plasma Chemistries^a	LO/HI/N^b	Mild (Grade 1)	Moderate (Grade 2)	Severe (Grade 3)
Glucose (mmol/L)	LO	3.61-3.38	3.05-3.60	≤ 3.04
	HI ^c	5.55-6.11	6.12-6.94	>6.94
	HI ^d	6.11-6.94	6.95-11.10	>11.10
Blood urea nitrogen (mmol/L)	HI	8.2-9.3	9.4-11.1	>11.1
Creatinine (μmol/L)	N	133-150	151-177	>177
Calcium (mmol/L)	LO	2.00-2.10	1.87-1.99	<1.87
	HI	2.62-2.74	2.75-2.87	>2.87
Magnesium (mmol/L)	LO	0.53-0.62	0.45-0.52	<0.45
Phosphorus (mmol/L)	LO	0.74-0.81	0.65-0.73	<0.65
Cholesterol (mmol/L)	HI	5.20-5.43	5.44-5.82	>5.82
Coagulation				
Fibrinogen (μmol/L)	HI	11.76-14.70	14.71-17.65	>17.65
	LO	4.41-5.88	3.68-4.40	<3.68

^a Depending upon the laboratory used, reference ranges, eligibility ranges and grading may be split out by sex and/or age.

^b Low, High, Not Graded.

^c Fasting.

^d Non-fasting.

VITAL SIGNS TOXICITY GRADING

Grading scale used for vital signs is according to DMID Toxicity Tables (2014)

Vital Signs	LO/HI/N ^a	Mild (Grade 1) ^b	Moderate (Grade 2)	Severe (Grade 3)
Fever (°C) ^c	HI	38.0-38.4	38.5-38.9	>38.9
Fever (°F)	HI	100.4-101.1	101.2-102.0	>102.0
Tachycardia	HI	101-115 bpm	116-130 bpm	>130 bpm or ventricular dysrhythmias
Bradycardia	LO	50-54 or 45-50 bpm if baseline <60 bpm	45-49 or 40-44 bpm if baseline <60 bpm	<45 or <40 bpm if baseline <60 bpm
Hypertension (systolic) - mm Hg ^d	HI	141-150	151-160	>160
Hypertension (diastolic) - mm Hg	HI	91-95	96-100	>100
Hypotension (systolic) - mm Hg	LO	85-89	80-84	<80
Tachypnea - breaths per minute	HI	23-25	26-30	>30

^a Low, High, Not Graded.

^b If initial bound of grade 1 has gap from reference range or eligibility range, calculations based on the New England Journal of Medicine (NEJM) reference ranges.

^c Applies to all temperature routes.

^d Assuming subject is awake, resting, and supine; for adverse events, 3 measurements on the same arm with concordant results.

4. TOXICITY TABLES FOR USE IN TRIALS ENROLLING CHILDREN GREATER THAN 3 MONTHS OF AGE

The abbreviations used in the following tables are:

ALT: alanine aminotransferase; AST: aspartate aminotransferase; CNS: central nervous system; CK: creatine kinase; hpf: high power field; GGT: gamma glutamyltransferase; mEq: milliequivalent; PT: prothrombin time; PTT: partial prothrombin time; ULN: upper limit of normal

CLINICAL ADVERSE EVENTS

Grading scale used for clinical adverse events is adapted from the DMID Pediatric Toxicity Tables for Children Greater Than 3 Months of Age (2007). For adverse events not included in the tables below, refer to the severity criteria guidelines in Section 12.1.3 of the CTP¹.

Gastrointestinal	Grade 1	Grade 2	Grade 3
Nausea/vomiting	Minimal symptoms; caused minimal or no interference with work, school or self-care activities	Notable symptoms; required modification in activity or use of medications; did not result in loss of work or cancellation of social activities	Incapacitating symptoms; required bed rest and/or resulted in loss of work or cancellation of social activities
Diarrhea	Slight change in consistency and/or frequency of stools	Liquid stools	Liquid stools greater than 4x the amount or number normal for the child
Appetite	-	Decreased appetite	Appetite very decreased, no solid food taken
Abdominal Pain	Mild	Moderate; no treatment needed	Moderate; treatment needed
Constipation	Slight change in consistency/frequency of stool	Hard, dry stools with a change in frequency	Abdominal pain
Reactogenicity	Grade 1	Grade 2	Grade 3
Local reactions			
Pain/tenderness at injection site	Aware of symptoms but easily tolerated; does not interfere with activity; discomfort only to touch	Notable symptoms; required modification in activity or use of medications; discomfort with movement	Incapacitating symptoms; inability to do work or usual activities; significant discomfort at rest
Erythema/redness	< 10 mm	10-25 mm	26-50 mm
Induration/swelling	< 10 mm	10-25 mm	26-50 mm
Itching at the injection site	Infrequent, brief episode of scratching, easily distracted from scratching	Frequent, longer episodes of scratching, difficult to distract	Near constant scratching, or scratching during sleep; excoriation of skin
Edema	< 10 mm	10-25 mm	26-50 mm
Rash at the injection site	< 10 mm	10-25 mm	26-50 mm
Systemic reactions			
Allergic reaction	Pruritus without rash	Pruritic rash	Mild urticaria

Headache	Minimal symptoms; caused minimal or no interference with work, school or self-care activities	Notable symptoms; required modification in activity or use of medications; did not result in loss of work/school or cancellation of social activities	Incapacitating symptoms; required bed rest and/or resulted in loss of work/school or cancellation of social activities
Fatigue/malaise	Minimal symptoms; caused minimal or no interference with work, school or self-care activities	Notable symptoms; required modification in activity or use of medications; did not result in loss of work/school or cancellation of social activities	Incapacitating symptoms; required bed rest and/or resulted in loss of work/school or cancellation of social activities
Myalgia	Minimal symptoms; caused minimal or no interference with work, school or self-care activities	Notable symptoms; required modification in activity or use of medications; did not result in loss of work/school or cancellation of social activities	Incapacitating symptoms; required bed rest and/or resulted in loss of work/school or cancellation of social activities
Arthralgia	Minimal symptoms; caused minimal or no interference with work, school or self-care activities	Notable symptoms; required modification in activity or use of medications; did not result in loss of work/school or cancellation of social activities	Incapacitating symptoms; required bed rest and/or resulted in loss of work/school or cancellation of social activities
Chills	Minimal symptoms; caused minimal or no interference with work, school or self-care activities	Notable symptoms; required modification in activity or use of medications; did not result in loss of work/school or cancellation of social activities	Incapacitating symptoms; required bed rest and/or resulted in loss of work/school or cancellation of social activities
Central Nervous System (CNS)	Grade 1	Grade 2	Grade 3
Generalized CNS Symptoms			Dizziness
Level of activity		Slightly irritable OR slightly subdued	Very irritable OR lethargic
Visual		Blurriness, diplopia, or horizontal nystagmus of <1 hour duration, with spontaneous resolution	More than 1 episode of Grade 2 symptoms per week, or an episode of Grade 2 symptoms lasting more than 1 hour with spontaneous resolution by 4 hours, or vertical nystagmus
Myelopathy		None	None
Peripheral Nervous System	Grade 1	Grade 2	Grade 3
Neuropathy/Lower Motor Neuropathy		Mild transient paresthesia only	Persistent or progressive paresthesias, burning sensation in feet, or mild dyesthesia; no weakness; mild to moderate deep

			tendon reflex changes; no sensory loss
Myopathy or Neuromuscular Junction Impairment	Normal or mild (<2 x ULN) CK elevation	Mild proximal weakness and/or atrophy not affecting gross motor function. Mild myalgias with/without mild CK elevation (<2 x ULN)	Proximal muscle weakness and/or atrophy affecting motor function with/without CK elevation; or severe myalgias with CK>2 x ULN
Other	Grade 1	Grade 2	Grade 3
Fever	38.0-38.4 °C or 100.4-101.1 °F	38.5-40 °C or 101.2-104.0 °F	Greater than 40 °C or 104.0 °F
Cutaneous	Localized rash	Diffuse maculopapular rash	Generalized urticaria
